At week 24 and week 36, we propose to utilize a portion of the blood sample to examine neurally derived blood exosomes as potential biomarkers. Exosomes are a class of endosome-derived membrane vesicles which are shed by neural cells and transported in blood plasma. Thus, they provide an accessible measure of proteins excreted by neuronal cells. Since two proteins, phosphorylated tau and beta-amyloid-42, are implicated in the formation of neurofibrillary tangles and amyloid plaques, they can potentially be used as biomarkers of disease status. Fiandaca et al. (2015) found that the concentrations of phosphorylated tau and beta-amyloid present within exosomes were significantly higher for AD patients than case controls and that they increased progressively with time and disease progression. We propose to examine, in this proof-of-concept trial, if these exosome biomarkers change as a result of L-serine treatment. Furthermore, we will assess whether the concentrations or presence of these biomarkers show any correlation with cognitive decline.

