3.3 Secondary Endpoints

The Institute of Ethnomedicine will also assess plasma neurally derived exosome protein levels of beta-amyloid, as a biomarker which may be related to cognitive decline in eAD (Fiandaca et al. 2015). Slopes reflecting the change in biomarker protein level will be compared between treatment and placebo groups. In addition, we will assess the relationship between the MoCA scores and the concentration of plasma neuronal derived exosome biomarkers (Fiandaca et al. 2015) to demonstrate that this biomarker is related to cognitive decline, and that the MOCA assessment and neural exosome biomarkers are useful for future studies.

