7.2 Statistical Methods

Nonparametric statistics are proposed since it is not known in advance if MoCA scores or levels of neurally-derived exosomes will approximate, or can be transformed, to a normal distribution. A Mann-Whitney U-test will compare exosomal protein levels or MoCA scores between the L-serine treatment and placebo patients at a $p < 0.05$ level. Parametric equivalents will be considered if appropriate to the distribution of the data.

First, we will check the effectiveness of the randomization by comparing the baseline characteristics of the L-serine and placebo groups according to demographic factors (e.g. age, gender). We will also assess whether the levels of biomarkers or cognitive impairment in the treatment group differ from the placebo group at time zero. This first test will check whether the randomization procedures were sufficient for the study. Next we will compare the exosomal protein levels or MoCA scores at the last study visit (month 9). (H_0 = there is no difference between the median exosomal protein level or MoCA score for treatment patients and control patients; H_1 = there is a difference between the median exosomal protein level MoCA score for treatment patients and control patients). A Mann-Whitney U-test will examine exosomal protein levels or MoCA scores of each patient, by comparing median values between groups. Second, we will assess the slope of the exosomal protein levels or MoCA scores over time to see if they differ among the treatment and control groups by Mann-Whitney U-test. We will use Spearman's Rank correlation, in which rho is the equivalent of the parametric correlation coefficient, to determine if there is a monotonic relationship between levels of proteins in the neurally-derived exosomes and the MoCA scores.

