7.3 Subject Population(s) for Analysis

The subject populations whose data will be subjected to the study analysis – both for the primary analysis and any applicable secondary analyses include:

Any subject randomized into the study that received at least one dose of study drug.

8 Safety and Adverse Events

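### The planned Spearman correlation of exosomal protein with MoCA has no term for arm, so for on-treatment data treatment effects on both measures can be read as a patient-level relationship

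*Combined protocol and SAP*

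**What the plan says.** Section 7.2 gives the analysis one sentence: "We will use Spearman's Rank correlation, in which rho is the equivalent of the parametric correlation coefficient", used "to determine if there is a monotonic relationship between levels of proteins in the neurally-derived exosomes and the MoCA scores". It mentions no arm, stratum or covariate, no visit, and no rule for pairing protein with MoCA. The sentence just before it, on slopes, does name the arms: they are compared "to see if they differ among the treatment and control groups by Mann-Whitney U-test".

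Section 7.3 sets one population for primary and secondary analyses: "Any subject randomized into the study that received at least one dose of study drug". Section 3.1 states the same aim, again without arm: "we will assess whether the concentrations or presence of these biomarkers show any correlation with cognitive decline". Section 3.3 says what the result is for: "to demonstrate that this biomarker is related to cognitive decline, and that the MOCA assessment and neural exosome biomarkers are useful for future studies".

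MoCA is scheduled at Day 0, week 24 and week 36. Section 3.1 places the exosome work at weeks 24 and 36, while 6.1 and 6.9 also list a baseline exosome sample. The correlation could therefore use baseline pairs, on-treatment pairs, or several pairs per patient.

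**The concern.** Section 3.3 makes a claim about patients: those with a different protein level also differ in cognition. A pooled Spearman correlation tests something wider, namely whether protein and MoCA are independent across the combined sample. At baseline, before randomized treatment can act, arm is not an issue. On treatment the two questions separate. If L-serine changes both measures, arm is a common cause, and the combined sample is correlated even when protein and MoCA are unrelated within each arm. The pooled rho then partly restates the two Mann-Whitney comparisons that 7.2 already plans. Pooling can also weaken or strengthen the evidence for a real within-arm relationship, depending on the direction of the treatment effects.

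At stake is whether the biomarker and MoCA are carried into later studies on evidence that may be only a difference between arms.

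**Working it through.** **Inputs from 7.1 and 7.2.** 20 patients per arm; protein SD 2.8 pg/ml, detectable difference 2.5 pg/ml at power 0.8; MoCA SD 4 points, detectable difference 3.65 points; alpha 0.05 (sidedness not stated, taken as two-sided).

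**Assumptions not in the documents.** Bivariate normal data within arm, MoCA rounded to whole points, no dropout, one on-treatment pair per patient, and within-arm correlations of 0, -0.4 or -0.45.

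**Step 1: the plan's own figures.** A two-sided t-test with 20 per arm has power 0.8 for 2.55 pg/ml and 3.64 points. At the stated 2.5 and 3.65 the power is 0.786 and 0.803. The stated differences reproduce. Section 7.1 gives no figure for the correlation itself.

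**Step 2: the correlation that arm alone induces.** In SD units the differences are d1 = 2.5/2.8 = 0.893 and d2 = 3.65/4 = 0.9125. With equal arms, arm adds d²/4 to each variance and d1·d2/4 to the covariance (negative when the shifts are in opposite directions). For within-arm correlation ρ,

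pooled r = (ρ ± d1·d2/4) / √[(1 + d1²/4)(1 + d2²/4)].

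Here d1·d2/4 = 0.204 and the denominator is √(1.199 × 1.208) = 1.204.

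- ρ = 0, protein down and MoCA up: -0.204/1.204 = -0.17.
- ρ = 0, half of each difference: -0.051/1.051 = -0.05.
- ρ = 0, one measure only: 0.
- ρ = -0.45, protein only: -0.45/√1.199 = -0.41.
- ρ = -0.45, protein down and MoCA up: -0.654/1.204 = -0.54.
- ρ = -0.4, both up: -0.196/1.204 = -0.16.

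**Step 3: rejection rates by simulation.** Pooled Spearman uses 38 df. The stratified version ranks within arm, centres the ranks within arm, combines them and uses 37 df. Rates come from runs of 10,000 to 40,000 replicates per scenario; separate runs agreed to within about 1.5 percentage points.

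| Within-arm correlation | L-serine minus placebo | Pooled | Stratified |
|---|---|---|---|
| 0 | none | 5% | 5% |
| 0 | protein -2.5 only | 5% | 5% |
| 0 | half of both differences | 6% | 5% |
| 0 | protein -2.5, MoCA +3.65 | 18% | 5% |
| -0.45 | none | 80% | 77% |
| -0.45 | protein -2.5 only | 71% | 77% |
| -0.45 | protein -2.5, MoCA +3.65 | 94% | 77% |
| -0.4 | protein +2.5, MoCA +3.65 | 13% | 66% |

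In the fourth row the simulated mean pooled rho is -0.17, matching Step 2. Adjusting the pooled ranks for arm (partial Spearman) gives 4.9% in that row. With ρ = -0.4 and no treatment effect, power is 68.4% pooled, 67.7% partial and 65.5% stratified.

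**The case against.** The strongest reply is that the plan never says it pools. Section 7.3 says whose data are eligible, and the same population feeds the Mann-Whitney tests, which do split by arm. Nor does 7.2 say the data are on-treatment, and a baseline correlation would raise no issue. This stands: pooling and on-treatment use are the natural reading, not a stated rule. But nothing in the documents provides for arm, and following the sentence literally gives a pooled rho.

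Second, a false relationship needs sizeable effects on both measures together, and a detectable difference is not an expected effect. This also stands and limits the size of the problem. The plan asks whether the biomarker changes; it does not assert that it will.

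Third, if L-serine acts on cognition through the protein, part of the between-arm correlation is real, and pooling has more power in the hoped-for case (94% against 77%). That is fair, and is a reason to keep the pooled rho in the report. But the pooled test cannot tell this mechanism from two unrelated treatment effects.

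A reader might infer larger distortions, for example by putting in the 7 pg/ml from 7.1 or by analysing change scores. The documents do not support either. The 7 pg/ml is a difference between preclinical AD and AD patients, not a treatment effect. The 7.2 sentence speaks of levels and scores, and no within-patient correlation is given from which to derive an SD of change.

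**Conclusion.** The point holds as a gap in the specification of a secondary analysis, and the gap affects the conclusion drawn in 3.3. Read naturally and applied to on-treatment values, the test can reject because the arms differ on both measures: about 18% against a nominal 5% at the plan's full detectable differences, about 6% at half of them, and 5% if only one measure is affected.

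A reader might also infer that pooling generally hides a real relationship. It does not. With an assumed within-arm correlation of -0.45, a protein-only shift of 2.5 pg/ml costs about 9 points of power (80% to 71%), and beneficial effects on both measures raise power. Marked masking, as in the last row of the table, needs treatment effects that oppose the within-arm correlation.

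The primary MoCA comparison is unaffected. The sizes rest on the assumed within-arm correlations, normality, no dropout and one pair per patient.

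**What to change.** In 7.2, before unblinding, specify for on-treatment values:

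- the visit, with one protein-MoCA pair per patient;
- the test: a Spearman correlation stratified by arm (ranks taken and centred within arm, then combined, 37 df with all 40 patients) or a partial Spearman adjusted for arm;
- each arm's rho alongside it, with the pooled rho kept as a description.

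In 3.3, do not let the statement of a patient-level relationship rest on the pooled rho alone. If a baseline-only correlation is intended, say so; it needs no stratification.

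The cost is a sentence or two of text and a few lines of code, with no new data or patients. Statistically it is one degree of freedom and, if L-serine affects neither measure, about 3 points of power for the stratified version (80% to 77%) or under 1 point for the partial version (68.4% to 67.7% in the -0.4 scenario).

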7.3 Subject Population(s) for Analysis

The subject populations whose data will be subjected to the study analysis – both for the primary analysis and any applicable secondary analyses include:

Any subject randomized into the study that received at least one dose of study drug.

8 Safety and Adverse Events

8.1 Definitions

Unanticipated Problems Involving Risk to Subjects or Others

Any incident, experience, or outcome that meets all of the following criteria:

- Unexpected in nature, severity, or frequency (i.e. not described in study-related documents such as the IRB-approved protocol or consent form, the investigators brochure, etc.)
- Related or possibly related to participation in the research (i.e. possibly related means there is a reasonable possibility that the incident experience, or outcome may have been caused by the procedures involved in the research)
- Suggests that the research places subjects or others at greater risk of harm (including physical, psychological, economic, or social harm).

Adverse Event

An **adverse event** (AE) is any symptom, sign, illness or experience that develops or worsens in severity during the course of the study. Intercurrent illnesses or injuries should be regarded as adverse events. Abnormal results of diagnostic procedures are considered to be adverse events if the abnormality:

- results in study withdrawal
- is associated with a serious adverse event
- is associated with clinical signs or symptoms
- leads to additional treatment or to further diagnostic tests
- is considered by the investigator to be of clinical significance

Serious Adverse Event

Adverse events are classified as serious or non-serious. A **serious adverse event** is any AE that is:

- fatal
- life-threatening
- requires or prolongs hospital stay
- results in persistent or significant disability or incapacity
- a congenital anomaly or birth defect
- an important medical event

Important medical events are those that may not be immediately life threatening, but are clearly of major clinical significance. They may jeopardize the subject, and may require intervention to prevent one of the other serious outcomes noted above. For example, drug overdose or abuse, a seizure that did not result in in-patient hospitalization or intensive treatment of bronchospasm in an emergency department would typically be considered serious.

All adverse events that do not meet any of the criteria for serious should be regarded as **non-serious adverse events**.

Adverse Event Reporting Period

The study period during which adverse events must be reported is normally defined as the period from the initiation of any study procedures to the end of the study treatment follow-up. For this study, the study treatment follow-up is defined as 30 days following the last administration of study treatment.

Preexisting Condition

A preexisting condition is one that is present at the start of the study. A preexisting condition should be recorded as an adverse event if the frequency, intensity, or the character of the condition worsens during the study period.

General Physical Examination Findings

At screening, any clinically significant abnormality should be recorded as a preexisting condition. Any new clinically significant findings/abnormalities that meet the definition of an adverse event must also be recorded and documented as an adverse event.

Post-study Adverse Event

All unresolved adverse events should be followed by the investigator until the events are resolved, the subject is lost to follow-up, or the adverse event is otherwise explained. At the last scheduled visit, the investigator should instruct each subject to report any subsequent event(s) that the subject, or the subject's personal physician, believes might reasonably be related to participation in this study. The investigator should notify the FDA of any death or adverse event occurring at any time after a subject has discontinued or terminated study

participation that may reasonably be related to this study. The FDA should also be notified if the investigator should become aware of the development of cancer or of a congenital anomaly in a subsequently conceived offspring of a subject that has participated in this study.

Abnormal Laboratory Values

Study lab results will be reviewed by the PI when results are available, prior to dispensation of the following visit study medication. The PI will make the determination of clinical significance of lab values that are out of normal range. Those of clinical significance will be reported as adverse events. No lab values are identified as exclusionary but the PI may withdraw a subject if they feel it is in the subject's best interest.

Hospitalization, Prolonged Hospitalization or Surgery

Any adverse event that results in hospitalization or prolonged hospitalization should be documented and reported as a serious adverse event unless specifically instructed otherwise in this protocol. Any condition responsible for surgery should be documented as an adverse event if the condition meets the criteria for and adverse event.

Neither the condition, hospitalization, prolonged hospitalization, nor surgery are reported as an adverse event in the following circumstances:

- Hospitalization or prolonged hospitalization for diagnostic or elective surgical procedures for a preexisting condition. Surgery should **not** be reported as an outcome of an adverse event if the purpose of the surgery was elective or diagnostic and the outcome was uneventful.
- Hospitalization or prolonged hospitalization required to allow efficacy measurement for the study.
- Hospitalization or prolonged hospitalization for therapy of the target disease of the study, unless it is a worsening or increase in frequency of hospital admissions as judged by the clinical investigator.

8.2 Recording of Adverse Events

At each contact with the subject, the investigator must seek information on adverse events by specific questioning, review of medical records, and, as appropriate, by

examination. Information on all adverse events should be recorded immediately in the source document, and also in the appropriate adverse event module of the case report form (CRF). All clearly related signs, symptoms, and abnormal diagnostic procedures results should be recorded in the source document, though should be grouped under one diagnosis.

8.3 Reporting of Serious Adverse Events and Unanticipated Problems

Investigators and the protocol sponsor must conform to the adverse event reporting timelines, formats and requirements of the various entities to which they are responsible, but at a minimum those events that must be reported are those that are:

- related to study participation,
- unexpected, and
- serious or involve risks to subjects or others

If the report is supplied as a narrative, the minimum necessary information to be provided at the time of the initial report includes:

- Study identifier
- Study Center
- Subject number
- A description of the event
- Date of onset
- Current status
- Whether study treatment was discontinued
- The reason why the event is classified as serious
- Investigator assessment of the association between the event and study treatment

8.3.1 Investigator reporting: notifying the Dartmouth IRB

This section describes the requirements for safety reporting by investigators who are Dartmouth faculty, affiliated with a Dartmouth research site, or otherwise responsible for safety reporting to the Dartmouth IRB. The Dartmouth College IRB (CPHS) requires expedited reporting of those events related to study participation that are unforeseen and indicate that participants or others are at increased risk of harm. The Dartmouth IRB will not acknowledge safety reports or bulk adverse event submissions that do not meet the criteria outlined below:

- Any adverse event (regardless of whether the event is serious or non-serious, on-site or off-site) that occurs any time during or after the research study, which in the opinion of the principal investigator is:

Unexpected (An event is “unexpected” when its specificity and severity are not accurately reflected in the protocol-related documents, such as the IRB-approved research protocol, any applicable investigator brochure, and the current IRB-approved informed consent document and other relevant sources of information, such as product labeling and package inserts.)

AND

Related to the research procedures (An event is “related to the research procedures” if in the opinion of the principal investigator or sponsor, the event was more likely than not to be caused by the research procedures.)

1. Unanticipated problems that are serious adverse events should be reported to the IRB within 1 week of the investigator becoming aware of the event.
2. Any other unanticipated problem should be reported to the IRB within 2 weeks of the investigator becoming aware of the problem.

Reporting Process

Unanticipated problems posing risks to subjects or others as noted above will be reported to the Dartmouth IRB using the form: “Unanticipated Problems Posing Risks to Subjects or Others Including Reportable Adverse Events” or as a written report of the event (including a description of the event with information regarding its fulfillment of the above criteria, follow-up/resolution and need for revision to consent form and/or other study documentation).

Copies of each report and documentation of IRB notification and receipt will be kept in the Clinical Investigator’s study file.

Reporting Deaths:

Concerning deaths that occur during the course of a research study:

- Report the event when the death is unforeseen (unexpected) and possibly related indicating participants or others may be at increased risk of harm. The AE/Unanticipated Problem Form is required.
- Report the event at the time of continuing review, for all other deaths, regardless of whether the death is related to study participation.

Other Reportable events:

For clinical drug trials, the following events are also reportable to the Dartmouth IRB:

- Any adverse experience that, even without detailed analysis, represents a serious unexpected adverse event that is rare in the absence of drug exposure (such as agranulocytosis, hepatic necrosis, Stevens-Johnson syndrome).
- Any adverse event that would cause the sponsor to modify the investigators brochure, protocol or informed consent form, or would prompt other action by the IRB to assure protection of human subjects.
- Information that indicates a change to the risks or potential benefits of the research, in terms of severity or frequency. For example:
 - An interim analysis indicates that participants have a lower rate of response to treatment than initially expected.
 - Safety monitoring indicates that a particular side effect is more severe, or more frequent than initially expected.
 - A paper is published from another study that shows that an arm of your research study is of no therapeutic value.
- Change in FDA safety labeling or withdrawal from marketing of a drug, device, or biologic used in a research protocol.
- Breach of confidentiality
- Change to the protocol taken without prior IRB review to eliminate apparent immediate hazard to a research participant.
- Incarceration of a participant when the research was not previously approved under Subpart C and the investigator believes it is in the best interest of the subject to remain on the study.
- Complaint of a participant when the complaint indicates unexpected risks or the complaint cannot be resolved by the research team.
- Protocol violation (meaning an accidental or unintentional deviation from the IRB approved protocol) that in the opinion of the investigator placed one or more participants at increased risk, or affects the rights or welfare of subjects.

